4.1.1 Definitions, Derivations and Classifications

Definition of Baseline

The baseline value for all endpoints (i.e., laboratory parameters and vital signs) will be the last available value prior to the first dose of study treatment in Trehalose group, and the date of first study visit in historical control group.

Assessments taken on the same day as study treatment will be assumed to be before study treatment unless indicated to be obtained post-study treatment.

Definition of Day 1

Study Day 1 is defined as the first day of study treatment in Trehalose group, and the date of first study visit in historical control group. This will also be considered the reference start date.

Definition of Study Day

Study Day will be computed as follows:

- Study Day = (Date of event – Date of study day 1) + 1 if the date of the event is on or after the date of study day 1.
- Study Day = (Date of event – Date of study day 1) if the date of the event is prior to the date of the study day 1.

Derivations Involving Dates

The number of days between two dates, the date of interest and the reference date, will be calculated as (Date of event – Reference date) + 1 when the event date is on or after the reference date; or, as (Reference date – Date of event) + 1 when the event date is before the reference date. The resulting value is then converted to years, months, or weeks, as appropriate. Partial dates will be imputed before calculating the number of days (See Appendix 2 for partial or unknown date imputation rules).

Common Calculations

Change from baseline (CHG) will be calculated as:

$$\text{Change from baseline} = \text{Actual (observed) value at post baseline visit} - \text{baseline value}$$

Percent change from baseline (PCHG) will be calculated as:

$$\text{Percent change from baseline (\%)} = 100 * (\text{Change from baseline at post baseline visit} / \text{Baseline value})$$

If baseline is not available, the change from baseline and percent change from baseline will not be calculated and will remain missing.

Demographics

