4.4.1 Demographic and Baseline Characteristics

Demographic data will be summarized descriptively including age (years) at time of first study treatment administration, age group (< 65 years, \geq 65 years), sex at birth, reproductive capacity, race, ethnicity and baseline physical measurements of height (cm), weight (kg), BMI (kg/m^2).

Baseline characteristics including ALS history, ALS diagnosis and ALS therapy as listed in items below will be summarized:

- Family history of ALS
- Site of onset (Limb, Bulbar, Axial, Respiratory, Generalized)
- Bulbar onset (Yes/No)
- Time since ALS symptom onset (months)
This equals to (date of first study treatment - date of ALS symptom onset + 1) / 30.4375
- Time since ALS diagnosis (months)
This equals to (date of first study treatment - date of ALS diagnosis + 1) / 30.4375
- Time since ALS symptom onset to diagnosis (months)
This equals to (date of ALS diagnosis – date of ASL symptom onset + 1) / 30.4375
- Has participant undergone genetic testing

- Has a genetic mutation been identified
- Type of identified mutation
- ALS Diagnosis made according to Revised El Escorial criteria
- Revised El Escorial Criteria for ALS
- Have genetically definite ALS
- Presence of tracheostomy (Yes/No)
- Presence of ventilation, noninvasive (NIV) (Yes/No)
- Gastrointestinal tube insertion (Yes/No)
- ALS medication use
 - None of Riluzole, Edaravone and Relyvrio
 - Any of Riluzole, Edaravone and Relyvrio (including subcategories: Riluzole, Edaravone, Relyvrio, Riluzole only, Edaravone only, Relyvrio only, Riluzole and Edaravone only, Edaravone and Relyvrio only, All of Riluzole, Edaravone and Relyvrio)
 - Neither Riluzole nor Edaravone, Both Riluzole and Edaravone

Participants' usage of these medications will be collected in concomitant medication form. These medications can be identified by the medication preferred term. Relyvrio is also called sodium phenylbutyrate/ursodoxicoltaurine, sodium phenylbutyrate/taurusodiol.

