4.4.2 Baseline Assessments

Descriptive statistics will be used to summarize, by treatment cohort and overall, the following baseline assessments in the FAS.

- ALSFRS-R Total Score
- ALSFRS-R Severity Group: All ALSFRS-R Items ≥ 2 , One or More ALSFRS-R Items < 2
- Pre-baseline ALSFRS-R Slope (points/month)
This equals to $(48 - \text{baseline ALSFRS-R total score}) / \text{Time since ALS symptom onset (months)}$
- % Predicted SVC
- ALSAQ – Symptom Index
- ALSAQ - Physical Mobility
- ALSAQ - Activities of Daily Living/Independence
- ALSAQ - Eating and Drinking
- ALSAQ – Communication
- ALSAQ - Emotional Reactions

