Appendix 2 Date Imputation Rules

The following rule will be used for missing/partial date imputation.

Item	Missing or Partial Date Variable	Imputation Rule
Adverse events, prior/concomitant medications and procedures	Start date	
The day is missing but month and year are available
 
 • If the month and year of occurrence are the same as month and year of the first study treatment, the start date will be set to the date of the first study treatment. • Otherwise, if the month and year of occurrence are not equal to the month and year of first study treatment, the start date will be set to the first day of the month of occurrence. 
The day and month are missing but year is available
 
 • If the year of occurrence is the same as the year of the first study treatment, the start date will be set to the date of the first study treatment. • Otherwise, if the year of occurrence is not the same as the year of the first study treatment, the start date will be set to January 1 of the year of occurrence. 
The start date is completely missing
 
 • The start date will not be imputed. • Adverse events will be considered treatment emergent unless the end date suggests otherwise. • Medications/Procedures will be considered both prior and concomitant unless the end date suggests otherwise. 
EXCEPTION: If complete end date is available and the imputed start date is greater than the end date, then the assumed start date should be set to the end date.

	End date	
The day is missing but month and year are available
 
 • If the participant died and the partial stop date is in the same month and year as the date of death, the end date will be set to the date of death. • Otherwise, the end date will be set to the last day of the month of occurrence. 
The day and month are missing but year is available
 
 • If the participant died and the partial end date is in the same year as the date of death, the end date will be set to the date of death. • Otherwise, the end date will be set to December 31 of the year of occurrence. 
The end date is completely missing
 
 • The end date will not be imputed.

		EXCEPTION: If the imputed end date is less than the start date, then the end date should be set to the start date.

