ALS	Symptom onset date, diagnosis date	
The day is missing but month and year are available
 
• Impute the missing day to be 15. 
The day and month are missing but year is available
 
• Impute the missing month and day to be July 1. 
The date is completely missing
 
• The date will not be imputed.

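### Partial ALS onset and diagnosis dates are imputed without an order check, so the baseline table and two propensity score covariates can take impossible or extreme values

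*SAP*

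**What the plan says.** SAP 4.1.3 lists ALS symptom onset and diagnosis dates among those to be imputed under Appendix 2. The ALS row of that appendix has two rules: "Impute the missing day to be 15" when only the day is missing, and "Impute the missing month and day to be July 1" when day and month are missing. No condition is attached to either.

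The rows for adverse events, medications and procedures do carry ordering exceptions. When a complete end date is available and an imputed start would fall after it, "then the assumed start date should be set to the end date". A matching exception covers imputed end dates.

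The imputed date goes straight into the derivations. SAP 4.1.1: "Partial dates will be imputed before calculating the number of days". SAP 4.4.1 defines time since onset as "This equals to (date of first study treatment - date of ALS symptom onset + 1) / 30.4375" and onset-to-diagnosis time as "This equals to (date of ALS diagnosis – date of ASL symptom onset + 1) / 30.4375". SAP 4.4.2 divides 48 minus the baseline ALSFRS-R total by time since onset to get the pre-baseline slope. None of these has a floor or a plausibility check.

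SAP 4.2.2 lists nine covariates for the propensity score. Time since onset, time since diagnosis and pre-baseline slope are three of them.

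**The concern.** The authors guarded against impossible date order in one part of Appendix 2 and left it open in the part that feeds the historical-control comparison. A ratio whose denominator can approach or cross zero is fragile in a logistic model, because one value can be many times larger than the rest. The propensity score determines the matches and strata behind the survival, ALSFRS-R and vital capacity comparisons. The standardized mean differences in SAP 4.4.3, which are meant to show whether balance was reached, use the same covariates. The onset-to-diagnosis interval is not in the listed score covariates, but it is reported in the baseline table.

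**Working it through.** The plan states no figure here to reproduce, so the check applies its own formulas.

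**Inputs.** From the SAP: the July 1 and day-15 rules (Appendix 2); months = (first dose - onset + 1)/30.4375 and onset-to-diagnosis = (diagnosis - onset + 1)/30.4375 (4.4.1); slope = (48 - baseline)/months (4.4.2). Assumed: onset recorded as 2023, imputed to 1 July 2023; baseline ALSFRS-R 36, so the numerator is 12; illustrative diagnosis and first-dose dates.

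**1. Onset-to-diagnosis time.** Diagnosis 15 March 2023 is 108 days before 1 July, so (-108 + 1)/30.4375 = -3.5 months. This needs only a year-only onset and a diagnosis before July 1 of that year, whenever treatment began.

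**2. Time since onset and slope, first dose in 2023.**

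| First dose | Days in 4.4.1 formula | Months | Slope (points/month) |
|---|---|---|---|
| 15 June | -15 | -0.49 | -24.4 |
| 30 June | 0 | 0 | undefined |
| 1 July | 1 | 0.033 | 365 |
| 20 July | 20 | 0.66 | 18.3 |
| 15 September | 77 | 2.53 | 4.7 |

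The result scales with the assumed baseline. For 24 to 42 points, the 20 July slope runs from 24/0.657 = 36.5 down to 6/0.657 = 9.1. Had the true onset been 31 January, the slopes for 15 June, 20 July and 15 September would be 2.7, 2.1 and 1.6.

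**3. Conflict with the general date rule.** SAP 4.1.1 changes its formula according to which date comes first, so an interval is never below one day. For 15 June it gives 16 + 1 = 17 days, 0.56 months and a slope of +21.5. The formula in 4.4.1 gives -24.4. The two sections differ in sign for the same participant.

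**4. Longer disease duration.** For onset on 15 January and first dose on 15 January one, two or four years later, the imputed slope is 1.84, 0.65 or 0.28, against 1.00, 0.50 or 0.25 from the assumed true onset. The distortion fades quickly.

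**5. The day-15 rule.** Diagnosis on the 3rd of the onset month gives (3 - 15 + 1)/30.4375 = -0.36 months from onset to diagnosis. The shift is about two weeks at most.

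**6. What one value does to a balance statistic.** In a group of n, one value at distance D from the mean of the others adds D²/n to the sample variance. Take n = 70 and assume the others average 0.5 to 1.0 points/month (the two-year and one-year values in step 4). A value of 18.3 gives D of 17.8 to 17.3, so the group SD is at least D/√70 = 2.1, however tight the other 69 are, and the mean moves by D/70 = 0.25. A value of -24.4 gives an SD of at least 3.0 and moves the mean by -0.36. An SD inflated in this way can hide a real imbalance in a standardized mean difference.

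**The case against.** A reader might infer that onset after diagnosis is what makes the slope negative. The documents do not support that: the slope's denominator runs from onset to first dose, not to diagnosis. A negative slope needs a year-only onset in the same calendar year as Day 1, and Day 1 before June 30. That is a much narrower set of participants.

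Such cases should be rare. Protocol 6.5 has the investigator document both dates at screening. Cohort 2 had already completed the Regimen E RCT, and the OLE where available (Protocol 4.1), so onset in the same year as an early-year first EAP dose is hardly possible there. The exposure is mainly recent-onset Cohort 1 participants.

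A reader might also infer that historical controls suffer in the same way, or that the day-15 rule can produce extreme slopes. The first is not shown: the documents do not say whether the external database holds calendar dates, partial dates or ready-made intervals. The second would need onset and Day 1 within weeks of each other.

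Finally, SAP 4.2.3, 4.2.4 and 4.4.3 call for balance and overlap checks, where an extreme slope might be noticed, and SAP Section 2 makes all comparisons exploratory. This limits the consequence. It does not repair a rule that yields impossible values, and step 6 shows that the balance statistic can itself be blunted by the value it should reveal.

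**Conclusion.** The gap is real and worth correcting, but its reach is limited. As written, the SAP can give negative onset-to-diagnosis times in the baseline table and, under narrower conditions, extreme, undefined or negative pre-baseline slopes in the propensity score. Sections 4.1.1 and 4.4.1 also disagree once imputed onset falls after first dose.

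The slope figures rest on assumed dates and an assumed baseline of 36. The number of partial dates is not given, so neither the number of affected participants nor the effect on matching can be sized. It would go too far to say that the matched comparison is invalid. What the documents support is that a few such values could distort the score and the standardized mean differences.

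**What to change.** Replace the ALS row of Appendix 2 with one rule: impute diagnosis first, then onset, each to the midpoint of its feasible interval. The interval starts at the earliest date consistent with the recorded year or month; for diagnosis, it starts no earlier than the earliest date the recorded onset allows. It ends at the earliest of the end of that year or month, Day 1 and, for onset, the diagnosis date. An empty interval means that the recorded dates conflict and should be queried.

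With no binding constraint, the rule still gives about July 1 or the 15th. In the example with diagnosis on 15 March, onset becomes 6 February and the slopes for 15 June, 20 July and 15 September become 2.8, 2.2 and 1.6.

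A check triggered only by onset falling after diagnosis would not be enough. With diagnosis on 5 July and first dose on 20 July, onset at 1 July passes that check and the slope stays at 18.3. The midpoint rule gives onset of about 3 April, 109/30.4375 = 3.58 months, and a slope of about 3.4.

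Also:
- State that the signed formulas in 4.4.1 override the general rule in 4.1.1 for these variables, so that any remaining date error shows as a negative value.
- Apply the same rule to historical controls where their calendar dates are partial, with the first study visit as Day 1.
- Report the number of imputed ALS dates by group.

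The cost is a few sentences in the SAP and slightly more programming. No new data are needed.

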Appendix 3 Calculation of % Predicted SVC

The % predicted SVC at each SVC measurement visit could be derived using the algorithm below:

1. Calculate the Predicted SVC.

Sex	Height (cm)	Age at SVC measurement (age_SVC)	Predicted SVC
Female	>=142.24	[18, 20)	(0.0699 * age_SVC) + (0.0416 * height) - 4.4470
		[20, 70)	(-0.0169 * age_SVC) + (0.0444 * height) - 3.1947
		[70, 89)	(-0.0296 * age_SVC) + (0.0313 * height) - 0.1889
		Other	Missing
	Other	Any	Missing
Male	>=147.32 and <= 203.2	[18, 25)	(0.0739 * age_SVC) + (0.0590 * height) - 6.8865
		[25, 86)	(-0.0298 * age_SVC) + (0.0844 * height) - 8.7818
		Other	Missing
	Other	Any	Missing

Where age_SVC = floor((intck("month", date of birth date, date of measurement) - (day(date of measurement) < day(date of birth))) / 12).

2. For each visit, set max_SVC = the maximal SVC result from multiple measurements
3. For each visit, % predicted SVC = 100 * max_SVC / Predicted SVC, round to 1 decimal.

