6.6.9 Slow Vital Capacity (SVC)

The vital capacity (VC) will be determined using the upright slow VC (SVC) method. All evaluators performing SVC must be NEALS certified. The SVC will be measured using the study-approved portable spirometer, and assessments will be performed using a face mask. A printout from the spirometer of all VC trials will be retained. Only the 3 best trials are recorded on the CRF. At least 3 measurable VC trials must be completed to score VC for all visits after screening. Predicted VC values and percent-predicted VC values will be calculated using the Quanjer Global Lung Initiative equations.

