The clinical safety profile of trehalose and the nonclinical toxicology data support the investigation of SLS-005 as a potential treatment of ALS. Weekly dosing of SLS-005 is the only regimen to be evaluated in clinical trials to date (participants with OPMD and SCA3) and will be used in this trial. Participants with either sporadic or familial ALS accumulate TDP43 and participants with the superoxide dismutase (SOD) mutation accumulate SOD aggregates and thus have the potential to benefit from treatment with SLS-005 through activation of autophagy.

The is an intermediate expanded access protocol (EAP) trial to provide access to the investigational product, SLS-005, to participants with ALS who are not eligible to participate in clinical trials. The results might be included in a regulatory submission.

This statistical analysis plan (SAP) describes the detailed procedures for the planned statistical analyses of the efficacy, safety, and biomarker data that are collected. The endpoints are defined, and the statistical methods used to analyze them are presented. Table shells for the planned tables, figures, and listings (TFL) are included in a separate document, entitled “Data Presentation Plan” (DPP).

This version of the SAP has been developed using protocol version 1.0, dated 31 July 2023. Changes from the statistical methodology planned in the protocol are described in Section 7.

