4.2.1 Eligible Historical Control Analysis Set

The eligible historical control analysis set will be constructed from the available databases relating to clinical outcomes in ALS consisting of previous ALS clinical research study participants who:

- met major eligibility criteria from this EAP study if related information was collected in historical database, including:
 - Inclusion criteria 2: Age 18 years or older.
 - Exclusion criteria 2: Screening glucose ≥ 140 mg/dl
 - Exclusion criteria 6: Screening body weight > 144 kilograms
- and had known mortality information
- and had baseline and at least one post-baseline ALSFRS-R total scores recorded
- and/or had baseline and at least one post-baseline measurements of Vital Capacity (VC) including the collected SVC or Forced Vital Capability (FVC)

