4.2.2 PS Estimation

PS method will be used to balance the population-level baseline characteristics between the Trehalose treated group and the eligible historical control analysis set. In order to calculate PS, the following selected common baseline demographics and characteristics variables of known prognostic significance will be used as covariates in PS estimation if applicable, other covariates may also be included.

- Age (years) [19]
- BMI (kg/m^2)
- Bulbar onset (Yes/No)
- Riluzole use (Yes/No)
- Time since ALS symptom onset (months) [19]
- Time since ALS diagnosis (months)
- Baseline ALSFRS-R total score
- Pre-baseline ALSFRS-R slope (points/month) [20]
- Baseline % predicted VC [21]

PS is the probability of a participant being assigned to a treatment instead of the other one conditional on a given set of baseline characteristics. It is determined by a logistic regression with all above common baseline covariates. To reduce any potential bias due to rare events, PS will be estimated using penalized maximum

likelihood estimation (PMLE) (Firth, 1993). The PS will be estimated for participants from Trehalose group and the eligible historical control analysis set. Overlap of PS between both groups will be assessed using standardized mean differences table and/or plot.

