4.7.3 SVC

4.7.3.1 Definition of Endpoints

The endpoint is the mean change from baseline in % predicted SVC (or VC) at Week 24.

For this EAP study, the SVC is measured at Screening/Baseline and Week 24 visit with the 3 best trials recorded on the eCRF. The % predicted SVC value will be calculated at each visit for analysis following the calculation algorithm in Appendix 3. For historical control group, the % predicted VC (based on collected SVC or FVC) will be used.

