7. CHANGES FROM AND ADDITIONS TO METHODS PLANNED IN THE PROTOCOL

The protocol Section 9.0 mentioned: for cohort 2, the TEAEs and biomarker NfL levels data collected during the parent HEALEY ALS Platform Trial Regimen E study will be combined with cohort 2 data in this EAP study for final analyses.

Changes in SAP: this is re-evaluated by sponsor and decided that the Regimen E study data will not be included in the analysis plan provided by Everest. The integration analysis of EAP study and Regimen E study data may be scheduled in-house by sponsor.

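### SAP Appendix 3 takes the place of the protocol's Global Lung Initiative equations without declaring the change, and no equation is named for the historical controls, so % predicted VC is not assured a common scale

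*SAP*

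**What the plan says.** Protocol 6.6.9, on slow vital capacity (SVC), names the reference set: "Predicted VC values and percent-predicted VC values will be calculated using the Quanjer Global Lung Initiative equations".

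SAP 4.7.3.1 gives a different instruction for this study's participants: "The % predicted SVC value will be calculated at each visit for analysis following the calculation algorithm in Appendix 3". Appendix 3 begins "The % predicted SVC at each SVC measurement visit could be derived using the algorithm below" and lists formulas by sex and age band, each linear in age and height. It gives no name or citation and does not mention GLI.

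For the comparison group, SAP 4.7.3.1 says only: "For historical control group, the % predicted VC (based on collected SVC or FVC) will be used". SAP 4.2.1 likewise accepts either SVC or forced vital capacity (FVC) from controls. Neither section gives a reference equation or a rule for recalculation.

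On departures from the protocol, SAP Section 1 says: "Changes from the statistical methodology planned in the protocol are described in Section 7". Section 7 contains one item, the exclusion of parent-trial data: "Changes in SAP: this is re-evaluated by sponsor and decided that the Regimen E study data will not be included".

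Baseline % predicted VC is one of the nine covariates listed for the propensity score in SAP 4.2.2. In SAP 4.7.3.2, change in % predicted VC at Week 24 is the outcome of the matched comparison, with the baseline value as a fixed effect.

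**The concern.** Percent predicted is a ratio of measured litres to a reference value. If the two groups use different reference values, identical lungs give different percentages. Subtracting baseline does not remove the problem, because the change is divided by the same reference value and is rescaled with it.

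The effect is not confined to the VC endpoint. Baseline % predicted VC enters the propensity score, which determines the 1:1 matches and the strata used for overall survival and ALSFRS-R. The balance check in SAP 4.4.3 compares recorded percentages, so it could look satisfactory while the underlying lung function differed.

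The SAP plans no formal hypothesis testing. It does report p-values for these comparisons, and its introduction says the results might enter a regulatory submission.

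**Working it through.** The plan gives no figure to reproduce. The check compares the instructions, shows what a scale mismatch would do, and evaluates the Appendix 3 formulas.

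**1. The instructions side by side**

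| Item | Protocol | SAP |
|---|---|---|
| Equation, EAP participants | GLI (6.6.9) | Appendix 3, unnamed and uncited (4.7.3.1) |
| Equation, controls | none stated | none stated (4.2.1, 4.2.2, 4.7.3) |
| Recalculation of control values | not stated | not stated |
| Change declared | – | not in Section 7 |

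The opening line of Appendix 3 is permissive, but SAP 4.7.3.1 makes the algorithm binding, and only for this EAP. The version history names an external database as the source of controls, so their percentages cannot be presumed to follow Appendix 3.

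**2. Effect of a mismatch**

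Let the controls' reference value be (1 + e) times the Appendix 3 value for the same person. A percentage P is then recorded as P / (1 + e), and a decline D as D / (1 + e). The documents give neither e nor typical values, so the e values, the 70% level and the 12-point decline are all assumptions.

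| e | 70% reads | 12-point decline reads |
|---|---|---|
| +0.05 | 70 / 1.05 = 66.7% | 12 / 1.05 = 11.4 |
| −0.05 | 70 / 0.95 = 73.7% | 12 / 0.95 = 12.6 |
| +0.10 | 70 / 1.10 = 63.6% | 12 / 1.10 = 10.9 |
| −0.10 | 70 / 0.90 = 77.8% | 12 / 0.90 = 13.3 |

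At 10% the matching covariate moves by −6.4 to +7.8 points and the change score by −1.1 to +1.3 points, with no real difference between the groups.

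**3. Minor: behaviour of the Appendix 3 formulas**

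Predicted SVC for women, in litres, with height h in cm:
- Age 69: −0.0169 × 69 + 0.0444h − 3.1947 = 0.0444h − 4.3608
- Age 70: −0.0296 × 70 + 0.0313h − 0.1889 = 0.0313h − 2.2609

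With SVC unchanged at 2.0 L (assumed):

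| Height | Predicted, 69 | Predicted, 70 | % predicted, 69 to 70 |
|---|---|---|---|
| 150 cm | 2.299 L | 2.434 L | 87.0% to 82.2% |
| 160 cm | 2.743 L | 2.747 L | 72.9% to 72.8% |
| 175 cm | 3.409 L | 3.217 L | 58.7% to 62.2% |

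The two lines meet where 0.0131h = 2.0999, that is h = 160.3 cm. At 2.0 L the step is under 1 point from about 157.7 to 163.4 cm. It affects a change score only in a woman who turns 70 between Baseline and Week 24. If 40–50% of the 70 participants are women and 1–2% of those do so (both assumed), that is 70 × 0.40 × 0.01 = 0.28 to 70 × 0.50 × 0.02 = 0.70 participants.

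Appendix 3 also sets the value to missing for men aged 86 or over and women aged 89 or over. Protocol 4.1 sets no upper age limit.

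**The case against.** The strongest reply is that the documents do not prove a numerical difference. Neither prints the GLI equations, so a gap between them and Appendix 3 cannot be computed. The protocol sentence is also in the assessments section, not the statistical section, and might describe scoring at the sites, while the SAP defines the value for analysis. Part of the SAP's front matter is not available, so an earlier history entry on the equation cannot be excluded.

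These points limit what can be said about size. They do not reconcile the texts. If the sponsor considers Appendix 3 equivalent to GLI, or intended only for analysis, the SAP should say so and give a source. Section 7, where the SAP says such changes are recorded, is available and silent.

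A second reply concerns weight. VC is exploratory and third in the protocol's order of priority, p-values are unadjusted, and VC is one of nine propensity-score covariates. Even an assumed 10% mismatch moves the 12-point decline by little more than 1 point. This is fair and keeps the point below the most serious grade. The shift in the matching covariate is larger, and its effect on the survival and ALSFRS-R comparisons is unknown.

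Third, the SAP is open about mixing SVC and FVC, and the paper it cites for this covariate calls the two similar in its title. That bears on the measure, not on the reference equation. The age-70 step and the upper-age rule are indeed small and would not justify a change alone.

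**Conclusion.** The concern holds. The SAP's rule for EAP participants conflicts with the method named in the protocol, the departure is not declared where the SAP says departures are declared, and no equation or recalculation rule covers the controls. As written, the plan permits treated and control values on different scales; it does not establish that they are.

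The size is conditional on the assumptions. For an illustrative 70% level and 12-point decline, a 5% difference in reference values shifts the level by −3.3 to +3.7 points and the decline by about 0.6 points. A 10% difference shifts them by −6.4 to +7.8 points and by 1.1 to 1.3 points. The resulting effect on matching, survival and ALSFRS-R cannot be derived from the documents. The age-70 discontinuity would be expected to touch fewer than one participant. The plan should be corrected, but because the analyses are exploratory this is not a fatal flaw.

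**What to change.** - Replace Appendix 3 with the protocol's GLI equations or, if Appendix 3 is kept, cite its source and declare the change in SAP Section 7.
- Name that one equation for both groups in SAP 4.2.2 and 4.7.3.1. Apply it to raw litres, age, sex and height in EAP and control participants before the propensity score is estimated.
- Where controls lack raw litres or height, report how many, say whether supplied percentages are used, and add a sensitivity analysis restricted to controls with recomputed values.
- State that controls measured by FVC still differ in measure from the EAP's SVC, which a common equation does not remove.

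The cost is SAP wording and one derivation program. If the propensity score has already been estimated, the score, the matching, the strata and the survival, ALSFRS-R and VC comparisons must be rerun. Some controls may not have the raw data; the documents do not show how many.
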